8.3 Endpoints and Analysis

8.3.1 Primary Endpoints

The primary endpoints are the incidence of the following AESI:

- Malignancies (excluding NMSC)
- Mortality
- Opportunistic infections and other infections of interest (Appendix 1)
- NMSC
- Serious psychiatric events (Appendix 2)
- Serious infections

8.3.2 Analysis of Primary Endpoints

In addition to analyses that consider initial treatment group (BENLYSTA cohort vs. comparison cohort), analyses that specifically account for changes in therapy (in either group) by considering a variety of risk windows will be employed. These analyses will attribute events to BENLYSTA treatment if they occur within the designated risk windows for BENLYSTA exposure and to comparison treatment otherwise. These analyses will allow for a registry patient to contribute person-time to both BENLYSTA treatment, and comparison treatment and as a result, will specifically account for treatment switching to BENLYSTA or from BENLYSTA. Switching between BENLYSTA and comparison treatment will be taken into account in a number of ways in the analysis and will be further defined within the statistical analysis plan. No new analyses for changing between BENLYSTA formulation or stratifying by BENLYSTA formulation are planned. Planned analyses are outlined below; all analyses will be detailed in the statistical analysis plan.

- Analysis by initial treatment group of rate per person years of observation time.
- Analysis by initial treatment group of rate per person years of exposure where BENLYSTA exposure ends 14 weeks (approximately 5 half-lives) after cessation of treatment.
- For serious psychiatric events, BENLYSTA exposure is all time on treatment with BENLYSTA ending 14 weeks (approximately 5 half-lives) after cessation of treatment, with all remaining treatment time attributed to the comparison cohort.
- For serious infections, opportunistic infections and other infections of interest, BENLYSTA exposure is all time on treatment with BENLYSTA ending 6 months after cessation of treatment, with all remaining treatment time attributed to the comparison cohort.
- For NMSC and malignancies excluding NMSC, analysis will be performed where all events will be attributed to BENLYSTA if the patient was ever exposed to BENLYSTA treatment prior to the event and attributed to the comparison cohort otherwise (ie, once exposed, always at risk).
- Mortality will be analyzed applying all the above-mentioned risk windows (eg, 14 weeks, 6 months, and ever-exposed).
- Other risk windows (including risk windows for comparison treatment) may also be assessed and defined in the statistical analysis plan.

Additional safety analysis will be performed comparing BENLYSTA treatment initiators with patients from the comparison cohort that start or switch an immunosuppressant and that have comparable background medication and treatment history. Subgroup analysis will be performed that will include but not be limited to analysis of patients with positive anti-dsDNA and low complement at baseline, patients with SLEDAI 2000 score at baseline (< 10 vs ≥ 10), SDI (0 vs ≥ 1), steroid use (yes vs no; ≤ 7.5 mg/day vs > 7.5 mg/day), immunosuppressant use (yes vs no; mycophenolate vs immunosuppressant other than mycophenolate), region (US/Canada vs Europe vs other), and race (black race vs other). Safety analyses will be adjusted for potential confounding factors ([Appendix 7](#)) through propensity score methods or other appropriate statistical methods. No new analyses for changing between BENLYSTA formulation or

stratifying by BENLYSTA formulation are planned. Further details of the safety analyses will be described in the statistical analysis plan.

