## **2. SUMMARY OF KEY PROTOCOL INFORMATION**

### **2.1. Changes to the Protocol Defined Reporting Analysis Plan and Previous RAP**

#### **2.1.1. Changes to the Protocol Defined Reporting Analysis Plan**

This RAP provides a more detailed elaboration of the high-level summary of statistical analysis provided in the protocol. There are no changes to the approach originally planned for statistical analysis. However, the following slight modifications have been made:

- Computation of rates (incidence and event) will be done separately for Opportunistic Infections and Other Infections of Interest (these were combined as one in the protocol).

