### 5.6.2. Examination of Subgroups

Descriptive summaries and statistical analyses will be performed separately for the two study cohorts (Current Users and Treatment Initiators).

Study Cohort	Definition / Criteria
Current Users	
 
• Subjects who have received or started qualifying medication(s) for <math>\geq 2</math> months (<math>\geq 62</math> days) prior to enrollment (Day 1)
 

Treatment Initiators	
 
• Subjects who have initiated or started qualifying medication(s) in the last 2 months (<math>< 62</math> days) prior to enrollment into the study (i.e Baseline SLE medication initiation <math>< 62</math> days from study Day 1)
 

*Study cohort can be determined for 'Eligible' subjects only (see section 4)*

For the purpose of study cohort assignment to either a current user or a treatment initiator, the following rules will be used to determine when a subject first received Benlysta and/or Non-Benlysta SLE medications:

- For BENLYSTA subjects: this will be the start date of earliest baseline Benlysta medication.

- For NON-BENLYSTA subjects: this will be the start date of study-qualifying non-benlysta SLE medications or the most recently added immunosuppressant if they are on multiple medications at baseline.

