## 7. STATISTICAL ANALYSES

The data displays of the final analysis are shown in Appendix 11. Unless otherwise specified, analyses will be performed using ‘Evaluable’ analysis population, and presented separately for ‘Current Users’ and ‘Treatment Initiators’ study cohorts.

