

- Calculation of an individual's subject-years of follow-up for each exposure strategy is shown in Appendix 2 (Section 9.2).

 
Incidence and event rates will be calculated and reported per 100 subject-years. The 95% CI for the rate will be calculated assuming an exact Poisson distribution method [Stokes, 2012].

Model Checking & Diagnostics

• No model-based statistical analysis will be performed; hence there is no model checking and diagnostics to be conducted.

Results Presentation
Total number of events, number and % of subjects with events, total subject-years at-risk, and total subject-years of follow-up will be reported. In addition, incidence proportion (where applicable), incidence rate, event rate and their 95% CI will be presented. The mock-shell tables showing details of data displays are presented in Appendix 12.
Subgroup Analyses
This analysis may be conducted for each study cohort separately (Current Users and Treatment Initiators; Section 5.6.2) . The list of TLF Data Displays is presented in Appendix 11.
Sensitivity Analyses
This analysis will also be conducted using the 'Evaluable Sensitivity' population. Details of the planned displays are provided in Appendix 11: List of TLF Data Displays.

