## 7.2. Effectiveness Analyses

Overview of planned selected effectiveness measures is shown in Table 3. The analyses will be conducted using ‘Evaluable’ analysis population and by study exposure defined using the ‘Initial Exposure’ strategy (see section 9.2.1.1) and/or by strata of clinical covariates listed in Section 5.6.1. Appendix 11: List of TLF Data Displays provides details of the analyses to be conducted.

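### The SAP delivers the protocol's initiator safety comparison only as crude tables, lists no AESI table for the protocol's named subgroups, and declares neither omission

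*Protocol*

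**What the plan says.** **Protocol 8.3.2** makes three commitments on the primary endpoints.

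- An initiator comparison: "Additional safety analysis will be performed comparing BENLYSTA treatment initiators with patients from the comparison cohort that start or switch an immunosuppressant". The sentence then sets a condition on who those comparators may be: "and that have comparable background medication and treatment history".
- Subgroups: "Subgroup analysis will be performed that will include but not be limited to analysis of patients with positive anti-dsDNA and low complement". The list continues with SLEDAI 2000, SDI, steroid use and dose, immunosuppressant use and type, region and race.
- Adjustment of the safety analyses for the confounders in Appendix 7. That list includes the names and durations of current SLE drugs (antimalarials, biologics, steroids, immunosuppressants) and steroid dose.

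**The SAP** states in 2.1.1: "There are no changes to the approach originally planned for statistical analysis". The one modification it lists is separate rates for opportunistic infections and other infections of interest.

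On study cohorts, SAP 5.6.2 is firm: "Descriptive summaries and statistical analyses will be performed separately for the two study cohorts (Current Users and Treatment Initiators"). Section 7 sets the Evaluable "analysis population, and presented separately for" the two cohorts, but only where nothing else is specified. For AESI rates, 7.1.5.1 is permissive: "This analysis may be conducted for each study cohort separately (Current Users and Treatment Initiators; Section 5.6.2"). Section 3.2 is permissive too.

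SAP 9.11.2 lists unweighted AESI tables for Treatment Initiators (for example 24.112, 24.122 and 24.212). SAP 9.11.4 lists weighted AESI tables 54.010 and 54.020 for the whole Evaluable population only.

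**The concern.** The two arms can differ in background treatment as well as in BENLYSTA use. The protocol says so: Section 1.3 names other background treatment as a confounder, and Section 1.1 links steroids and immunosuppressants to infection. An initiator comparison restricted to patients with similar treatment histories is the protocol's direct answer to that problem.

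It also addresses prevalent use. Current users started a qualifying drug at least 62 days before enrollment, so their baseline SLEDAI is measured after treatment began. Patients with past but not current BENLYSTA use are excluded. A weighted rate that pools current users with initiators may therefore be biased, in a direction that cannot be known in advance.

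As listed, the SAP yields no adjusted AESI result for initiators and no AESI result by any named subgroup. A reader of the final report would find SAP 2.1.1 saying that the approach had not changed.

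**Working it through.** **1. Commitments against deliverables**

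| Protocol 8.3.2 | SAP |
|---|---|
| Initiators against comparators who start or switch an immunosuppressant | Partly kept. 5.6.2 dates NON-BENLYSTA initiators from the qualifying drug, or from the latest immunosuppressant added if there are several. Starts or switches during follow-up are not covered. |
| Comparable background medication and treatment history | Not delivered. The initiator AESI tables in 9.11.2 involve no restriction, matching or weighting on background treatment. |
| AESI by named baseline subgroups | Not listed. 5.6.1 uses these factors for descriptive summaries, and the AESI subgroup row in 7.1.5.1 names only study cohort. The one other AESI split is the elderly summary (23.0001), and age is not among the named factors. |
| Adjustment for Appendix 7 confounders | Partly kept, through weighting of the pooled population. In Table 4 (9.9) the only SLE-drug term is corticosteroid use in the past six months, yes or no. |
| Declaration of changes | 2.1.1 mentions none of the above. |

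**2. What restricting to initiators buys**

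An initiator may have started up to 61 days before enrollment (SAP 5.6.2), and a SLEDAI up to 30 days after enrollment counts as baseline (SAP 5.2). It can therefore follow 61 + 30 = 91 days of treatment. Restriction shortens the gap but does not close it.

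**3. Planned precision, reproduced**

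Inputs from Protocol 8.2: 2,000 and 1,000 patients, 10% annual drop-out, 5 years, serious-infection rate 5.80 per 100 patient-years.

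- Years per patient = (1 − 0.9⁵)/(−ln 0.9) = 3.88675. This gives 7,773.5 and 3,886.8 patient-years (stated 7,773 and 3,886).
- Half-width = 100 × 1.96 × √(0.058/7,773 + 0.058/3,886) = 0.927 (stated ±0.93).
- The same formula gives 0.318 for deaths (stated ±0.32). For malignancy it gives 0.18 against a stated ±0.19, a last-digit difference that does not affect this point.

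**4. Precision in initiators (assumed shares)**

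The documents give no initiator share. With shares s_B and s_C of person-years, half-width = 100 × 1.96 × √(0.058/(7,773 s_B) + 0.058/(3,886 s_C)).

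| s_B, s_C | Serious-infection half-width |
|---|---|
| 75%, 75% | ±1.07 |
| 50%, 50% | ±1.31 |
| 30%, 30% | ±1.69 |
| 30%, 70% | ±1.33 |
| 70%, 30% | ±1.52 |

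The SAP reports arm-specific exact Poisson intervals, not differences. At expected count E, the limits are χ²(0.025; 2E)/2 and χ²(0.975; 2(E+1))/2, divided by person-years. At a 50% share, before any loss from weighting:

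- Serious infection: E = 0.058 × 3,886.5 = 225 and 0.058 × 1,943 = 113. The intervals are about 5.1 to 6.6 (BENLYSTA) and 4.8 to 7.0 (comparison).
- Malignancy excluding NMSC, at 0.226: E = 8.8 and 4.4. The intervals are 0.10 to 0.43 and 0.07 to 0.56.

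Serious infection stays informative; malignancy does not.

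**The case against.** The strongest reply is that the initiator contrast survives. Crude BENLYSTA against NON-BENLYSTA tables exist for Treatment Initiators under every exposure strategy, and dating comparators by their latest immunosuppressant partly captures starting or switching. This stands as far as it goes. What is missing is the comparability condition and any adjustment within initiators.

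Second, the by-cohort rule is not uniformly firm. Section 7 allows exceptions, 7.3.1 specifies the Evaluable population for the propensity analysis, and 3.2 and 7.1.5.1 use *may*. Only 5.6.2 is unconditional. This also stands, and leaves a wording conflict rather than a second substantive defect.

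Third, enlarging the pooled propensity model is debatable. For current users, steroid dose at enrollment may already reflect BENLYSTA, and steroid use is itself an effectiveness endpoint, so adjusting for it could remove part of an effect or add bias. This stands, and the fix leaves the pooled model alone.

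Fourth, the mock shells are in a separate file. Absence is therefore judged from the table list and the methods text. The listed titles make a hidden subgroup table unlikely, but it cannot be excluded.

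The protocol's deferral of detail to the SAP is a weaker defence. It permits elaboration of analyses that are to be done, not their unrecorded omission.

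**Conclusion.** The point holds. Two analyses that the protocol says will be done, the comparable-background initiator comparison and the named AESI subgroups, are not delivered by the listed tables, and SAP 2.1.1 does not record this. The study is descriptive with no hypothesis tests, so no error rate is at stake. What is lost is the planned protection against confounding and prevalent-user bias. The size of that bias cannot be computed: the documents give no initiator shares, background-treatment prevalences or rate ratios. The precision figures rest on assumed initiator shares and on the protocol's reference rates applying equally in both arms.

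Three stronger readings are not supported.

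- A reader might infer that the initiator comparison was removed altogether. The crude tables remain.
- A reader might infer that AESI were singled out, because SAP 7.2 allows effectiveness analyses "by strata of clinical covariates listed in Section 5.6.1". That wording is optional, and no effectiveness table is listed by those strata either.
- A reader might infer that Table 4 is wrong for the pooled analysis and must be replaced. The documents do not establish that, given the problem of terms measured after treatment began.

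**What to change.** 1. Add Treatment Initiator versions of the 53.x tables and of 54.010 and 54.020, with their own propensity model, balance checks and positivity checks. That model should add antimalarial use, prior SLE treatment history, steroid dose, and background immunosuppressants other than the newly started drug. A plain immunosuppressant yes/no term is unusable, because SAP 4.1 places every comparator on one. Apply the stop rule in SAP 7.3.1 to this model separately, so that a failure here does not cancel the pooled weighted tables. State whether starting or switching is judged at enrollment only or also during follow-up.
2. Add AESI rates by the baseline subgroups of Protocol 8.3.2, labelled descriptive and unweighted. Note that the stratum without immunosuppressants has no comparators, that patients with any SLEDAI item not done drop out of the total-score split (SAP 9.6.2.3), and that rare AESI will have few events. State the steroid category boundary used, since Protocol 8.3.2 and SAP 5.6.1 treat exactly 7.5 mg/day differently.
3. Reconcile SAP 5.6.2 and Section 7 with 3.2, 7.1.5.1 and 9.11.4 on when analyses are split by cohort.
4. Correct SAP 2.1.1 to record and justify any Protocol 8.3.2 analysis that will not be done.

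Keep Table 4 as the primary model for the pooled weighted tables. A pooled model with added background-treatment terms is at most an optional sensitivity analysis.

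**Cost.** No new data collection is needed: Protocol 6.1 and Appendix 7 already cover these variables. The work is derived variables, one further propensity model and extra tables. Intervals widen in initiators, rare AESI yield little, and the initiator model may fail its balance check.

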8.3.3 Effectiveness Endpoints and Analysis

Additional endpoints include the following:

- Organ damage as assessed by SLICC/ACR Damage Index ([Appendix 5](#))
- Concomitant SLE medications including steroids
- Hospitalizations

For any effectiveness endpoint analyses performed, methods to reduce the potential impact of confounding may be employed. These methods could include subgroup analysis, modeling adjusting for baseline and/or other confounding variables, or patient matching techniques like propensity score analysis. Furthermore, analyses considering changes in BENLYSTA use over time (eg, on or off treatment, but not changes between BENLYSTA formulations) in order to assess BENLYSTA effectiveness, as well as evaluate how these endpoints vary in response to BENLYSTA treatment will be assessed and further explored as appropriate. These analyses will be described in the statistical analysis plan.

9 Scientific Advisory Committee (SAC)

A Scientific Advisory Committee (SAC) consisting of global clinical experts, along with GSK staff (clinical, statistics, epidemiology) will be formed. The SAC will meet as needed to review the data collected.

10 Study Limitations

This is a registry and, as such, participants are not randomized into study arms. Due to the lack of randomization, there is a significant risk of confounding (ie, imbalance in important baseline characteristics between the BENLYSTA cohort and the comparison cohort where these characteristics are also risk factors for the outcomes). The present study attempts to minimize such confounding by selecting comparison patients that are as similar as possible to BENLYSTA cohort and will also attempt to account for confounding by further adjustment in the analysis using relevant statistical methods (such as propensity score matching or adjustment for baseline factors) (see Section 6.2). However, as with all non-randomized observational studies, residual unmeasured confounding may still exist. In addition, although the study is designed to specifically attempt to enroll a sample of SLE patients who are closely matched in both cohorts, it may be that the final enrolled study sample is not as well matched as desired due to multiple patient factors that can't be controlled for. The Sponsor will monitor enrollment for the proportion of patients who are treatment initiators versus current users and communicate to the sites the interest to achieve a reasonable balance for both groups.

Patients receiving commercially available belimumab may be seen more often by their medical care providers as compared to the bi-annual visits of standard of care patients. This may create

a reporting bias with increased reporting of events for some outcomes in the BENLYSTA group.

11 Study Administration

This study is sponsored by GlaxoSmithKline (GSK) LLC. They will lead on the operational conduct of this observational study world-wide working with contract research organizations.

11.1 Informed Consent

The consent form must be approved by the Institutional Review Board (IRB) or Institutional Ethics Committee (IEC) and contain all elements required by national, state, local, and institutional regulations or requirements. In the event that local regulations/laws require a Privacy Authorization this will be included as part of the informed consent process. Informed consent will be obtained by investigators for each patient whose data are included in this study. A copy of the signed informed consent must be given to each study patient.

11.2 Institutional Review Board Review/Independent Ethics Committee Review and Approval

Regulatory approval or notification will be obtained or performed, respectively, in countries where this is required. IRB/IEC approval will be obtained by participating investigators or a representative thereof; however, application will be made to central IRBs/IECs governing regions or countries wherever this is feasible.

11.3 Protocol Revisions

Protocol amendments will be prepared and approved by the sponsor. All protocol amendments will be signed by the investigator and submitted to the IRB/IEC for review prior to implementation. Documentation of IRB/IEC approval must be forwarded to the sponsor or designee. If an amendment significantly alters the study design or affects statements in the informed consent form, the informed consent form must be revised accordingly and submitted to the IRB/IEC for review and approval. The approved consent form must be used to obtain informed consent from new patients prior to enrollment and must be used to obtain informed consent from patients already enrolled if they are affected by the amendment.

11.4 Data Management

The investigator is responsible for maintaining accurate, complete, and up-to-date records for each patient. The investigator is also responsible for maintaining any source documentation related to the study, including any films, tracings, computer discs, or tapes.

The anonymity of participating patients must be maintained. For data collection and management purposes, patients are to be identified by a patient number only. Documents that identify the patient beyond patient number will not be submitted to the sponsor (eg, the signed informed consent document; patient initials) and must be maintained in strict confidence by the

investigator, except to the extent necessary to allow auditing by the regulatory authorities, study monitor, or sponsor representatives.

Site personnel record all data for each study patient through electronic case report forms (eCRFs) using an Electronic Data Capture (EDC) system provided and approved by the sponsor. Sites must complete the eCRFs in a timely manner and the investigator must promptly review the completed eCRFs for each patient. As the person ultimately responsible for the accuracy of all eCRF data, the investigator must sign the Investigator's Statement in each patient's eCRF.

The EDC system automatically generates queries resulting from the computer checks embedded into the system, so as to ensure accuracy, quality, consistency, and completeness of the database. Manual queries resulting from review by monitors, medical coders, and other Data Management staff are also generated from within the EDC system, where they are tracked. Sites resolve the queries and correct the entered data when necessary. Every change to data is captured in the EDC system audit trail. Upon completion of the study, or after reaching a pre-specified point in the study, Data Management will lock the database and generate the SAS datasets necessary for data analysis and reporting. Upon completion of the study, each site will be provided with the eCRFs for each of their patients.

